13 APPENDIX E - LABORATORY AND BLOOD PRESSURE VARIABILITY ASSESSMENTS

10-year ASCVD Risk Score Assessment:

Total Cholesterol, HDL-C and SBP values are used to calculate a 10-year ASCVD risk score, which is part of the initial TASS assessment to determine initial treatment eligibility. Since participants will only be eligible for treatment if their 10-year ASCVD risk score is 5% to <20%, no participant at Virtual Visit 1 will have a 10-year ASCVD risk score outside of this range with the exception of diabetics. A diabetic was required to have an ASCVD risk score of 0% to <20%. When using verified laboratory and BP data that is different from the data the participant entered into the Web App, the 10-year ASCVD risk score generated by the CMOG is highly likely to differ from the value generated by the participant. For the purpose of evaluating the first co-primary endpoint of the AUS, if the CMOG's initial TASS outcome is "Do Not Use" because the CMOG's 10-year ASCVD risk score is <5% or >20%, and no other "Do Not Use" warnings were identified, the participant's 10-year ASCVD risk score will be considered acceptable if the CMOG ASCVD risk score is 4% or greater. Diabetics are excluded from this variability assessment as 0% to <5% ASCVD risk score is acceptable. The rationale for not imposing an upper risk level is that all participants with a risk >5% are potential candidates for statin therapy. The only participants who should not be treated are those for whom the clinicians' assessments indicate they are too low risk. The lower risk for acceptability was set at >4% to account for variations in laboratory or blood pressure data that lead to a risk score slightly lower than 5%.

REF Assessment:

A REF is generated from the laboratory or BP values if one of the following criteria are met:

- TG and LDL-C REF criteria:

Lab	Values for a REF
TG	≥ 175 mg/dL
LDL-C	≥ 160 mg/dL
hs-CRP	≥ 2.0 mg/L

- Metabolic syndrome is also a potential REF and requires the laboratory and BP values to reach pre-specified thresholds. To obtain a REF for metabolic syndrome, 3 out of 4 of the following criteria need to be met:

Criteria (3 out of 4 must be met)	Value
Low HDL-C	Males: 20-39 mg/dL Females: 20-49 mg/dL
Elevated Triglycerides	150 - 174 mg/dL
Elevated Blood Pressure	Systolic blood pressure 130-180mmHg* OR Diastolic 85-120mmHg* OR Use of blood pressure medications ("yes")
Increased waist circumference	Males 40" and greater or Females 35" and greater - The waist circumference input is a yes/no response

*If SBP is 130-180mmHg AND DBP is 85-120mmHg, this only counts as a 1 of the 3 flags required to trigger a REF (not 2 separate flags).

The 2018 Cholesterol Treatment Guidelines outlines the different REFs and how they should be used when making treatment decisions. As previously stated, the laboratory and BP variability criteria for REFs will only be applied if the participant and CMOG initial TASS outcomes are different. Since the participant is only eligible for treatment following a "OK to Use" or "Ask a Doctor" (and indicated a doctor said it was okay to proceed) initial TASS outcome, this would require the CMOG to obtain a "Do Not Use" initial TASS outcome because of the lack of the REF generated by the participant. If this occurs, the variability criteria will be applied to the CMOG laboratory or BP value that generated a REF for the participant. If application of the variability criteria results in the laboratory or BP value meeting the REF criteria, the participant's REF will be considered acceptable.

Treatment Range Assessment:

Predefined laboratory and BP treatment ranges are part of the TASS assessment. The following values will result in a "Do Not Use" outcome by the TASS Tool:

Laboratory Parameter	Values for "Do Not Use" Outcome
TC	<130 or >320
TG	≥500
LDL – Male age 20-39	<160 or ≥190
LDL - Male age ≥40 to ≤75 Female age <50 or >75	<70 or ≥190
HDL	<20 or >100
SBP	<90 or >180
DBP	<50 or >120

Should the CMOG get a "Do Not Use" initial TASS outcome because a lab value was "out-of-range," the variability criteria will be applied to the "out-of-range" value(s). If the variability criteria result in a value within the appropriate treatment range, it will be considered acceptable.

The following reference was used to establish the acceptable level of variability between the laboratory parameters (Contois JH, et.al. Reliability of low-density lipoprotein cholesterol, non-high-density lipoprotein cholesterol, and apolipoprotein B measurements; Journal of Clinical Lipidology (2011) 5, 264–272.¹¹) for the evaluation of REFs and Range differences within the outcome assessments. The values were based on The National Cholesterol Education Program (NCEP) analytical performance goals for these tests.

Laboratory Parameter	Acceptable Level of Variability for Laboratory Values
Total Cholesterol	$\leq 9\%$
Triglycerides	$\leq 15\%$
LDL-C	$\leq 12\%$
HDL-C	$\leq 13\%$

No variability criterion will be applied for hs-CRP results.

Multiple factors can contribute to variability in these laboratory measurements over time. Examples include changes in diet, the time of day the sample was taken, whether the individual was fasting or non-fasting, and the laboratory or person performing the analysis. However, because of the difficulty in trying to account for these factors in addition to the analytical factors in the assessment of variability, we will rely solely on the analytical variability.

The acceptable variability for blood pressure measurements is more difficult to ascertain based on a review of the literature. Important factors that could impact variability include the timing of the BP measurement because of the circadian variability in BP, the use of a different device for the participant's inputted BP versus the clinical sites inputted BP, and operator variability when using manual devices. In light of these factors and taking into account that a normal circadian change in BP over the course of 24 hours could be 10% to 20%, we set the acceptable variability for BP at 15%.

Laboratory Parameter	Acceptable Level of Variability for Blood Pressure Values
Systolic Blood Pressure	$\leq 15\%$
Diastolic Blood Pressure	$\leq 15\%$

Procedure for Applying Laboratory and Blood Pressure Variability Criteria for Evaluation of the Overall Correct Initial TASS Outcome

If the participant and CMOG initial TASS outcomes agree, the laboratory and blood pressure variability is acceptable. If the initial TASS outcomes do not agree, it will be assessed whether this is due to laboratory or blood pressure variability using the following approach:

1. Assess whether the difference in initial TASS outcomes is due solely to a CMOG laboratory or blood pressure value being out-of-range. If this is true, the variability criteria will be applied to the CMOG laboratory or BP value to determine if the variability results in a value in the treatment range.
 - a. If the established variability is within treatment range, then the CMOG value is acceptable.
 - b. If the established variability is outside the treatment range, then the CMOG value is not acceptable.
2. Assess whether the difference in initial TASS outcomes is due solely to the CMOG 10-year ASCVD score being out of range. If this is true, apply the variability criteria to the CMOG 10-year risk score.
 - a. If the ASCVD risk score is within the designated range, then the CMOG total cholesterol, HDL-C and SBP values are acceptable.
 - b. If the ASCVD risk score is outside the designated range, then the CMOG total cholesterol, HDL-C and SBP are not acceptable.
3. Assess whether the difference in initial TASS outcomes is due solely to the CMOG laboratory or blood pressure data not generating a REF. If this is true, apply variability criteria to the CMOG laboratory or BP value to determine if the REF is generated.
 - a. If REF generated, then the CMOG values are acceptable.
 - b. If REF not generated, then the CMOG values are not acceptable.

14 APPENDIX F – IMPUTATION OF MISSING KEY DATES FROM THE TARGETED MEDICAL AND MEDICATION HISTORY FORM.

Scenarios	Day of Event [1]	Date Stopped Medication [2]	Date Spoke to the Doctor [2]	Imputation
Missing Date for Day Action Taken (Stopped Medication or Spoke to Doctor)	Yes	Only Month and Year	Yes	Date Stopped Medication imputed as the date halfway between date of the event and the end of the month
	Yes	Only Month and Year	Only Year	Date Stopped Medication imputed as the date halfway between date of the event and the end of the month. No imputation for Date Spoke to Doctor
	Yes	Only Year	Yes	No imputation for Date Stopped Medication
	Yes	Yes	Only Month and Year	Date Spoke to Doctor imputed as the date halfway between date of the event and the end of the month
	Yes	Yes	Only Year	No imputation for Date Spoke to Doctor
	Yes	Only Month and Year	Only Month and Year	Date Stopped Medication imputed as the date halfway between date of the event and the end of the month. Date Spoke to Doctor imputed as the date halfway between date of the event and the end of the month
	Yes	Only Year	Only Month and Year	No imputation for Date Stopped Medication Date Spoke to Doctor imputed as the date halfway between date of the event and the end of the month
	Yes	Only Year	Only Year	No imputation for Date Stopped Medication No imputation for Date Spoke to Doctor
Missing Date of the Event	Only Month and Year	Yes	Yes	Date of Event imputed as the date halfway between the beginning of the month and earliest date of action (i.e., earliest of the date medication stopped or spoke to doctor)
	Only Month and Year	Only Month and Year	Yes	Date of Event imputed as the date halfway between the beginning of the month and the date spoke to doctor. Date Stopped Medication imputed as the date halfway between date of

Scenarios	Day of Event [1]	Date Stopped Medication [2]	Date Spoke to the Doctor [2]	Imputation
				the event and the end of the month.
	Only Month and Year	Yes	Only Month and Year	Date of Event imputed as the date halfway between the beginning of the month and the date medication stopped. Date Spoke to Doctor imputed as the date halfway between date of the event and the end of the month
	Only Month and Year	Only Month and Year	Only Month and Year	Date of Event imputed as beginning of the month. Date of each action imputed as end of the month.
	Only Year	Yes	Yes	No imputation for Date of Event
	Only Year	Yes	Only Month and Year	No imputation for Date of Event Date Spoke to Doctor imputed as the date halfway between date of the stopped medication and the end of the month
	Only Year	Only Month and Year	Yes	No imputation for Date of Event Date Stopped Medication imputed as the date halfway between date of spoke to doctor and the end of the month.

[1] Event dates will be obtained from the Targeted Medical and Medication History Form or from the AE form of the respective AE. AE dates will be start dates of the event.

[2] Action dates only imputed if the participant took the respective action.

15 APPENDIX G - SCENARIOS FOR LDL-C VALUES AND INCLUSION OF VALUES IN PROPOSED ANALYSES OF LDL-C

Scenario	Primary LDL-C Analysis	Sensitivity Analyses				
		#1	#2	#3	#4	
*An LDL-C retest will be performed at Visit 2 and used for this analysis.						
^ Missing LDL-C value will be imputed according to missing data imputation method.						
"OK to Use" Outcome Scenarios						
1. Completes 6-month trial with an “OK to Use” outcome (based on participant’s outcome) and has entered an LDL-C value into the Web App during a reorder assessment verified by source document for Visit 2	X	X	X	X	X	
2. Completes 6-month trial with an “OK to Use” outcome (based on participant’s outcome) and has entered an LDL-C value into the Web App during a reorder assessment NOT verified by source document for Visit 2	X*	X*	X*	X*	X	
3. Completes 6-month trial with an “OK to Use” outcome (based on participant’s outcome) with an inadequate LDL-C response value entered into the Web App during an early reorder assessment but at a subsequent reorder assessment enters an adequate LDL-C response value into the Web App verified by source document for Visit 2	X	X	X	X	X	
4. Completes 6-month trial with an “OK to Use” outcome (based on participant’s outcome) with an inadequate LDL-C response value entered into the Web App verified by source document for Visit 2	X	X	X	X	X	
5. Completes 6-month trial with an “OK to Use” outcome (based on participant’s outcome) with a single inadequate LDL-C response value entered into the Web App NOT verified by source document for Visit 2	X*	X*	X*	X*	X	
6. Completes 6-month trial with an “OK to Use” outcome (based on participant’s outcome) and has NOT entered an LDL-C value into the Web App during a reorder assessment	X*	X*	X*	X*	-	
7. Has an “OK to Use” outcome with an LDL-C value entered into the Web App during an early reorder assessment verified by source document for Visit 2, but at a later reorder gets a “Do Not Use” or “Ask a Doctor” outcome	X	-	X	X	X	
8. Has an “OK to Use” outcome with an LDL-C value entered into the Web App during an early reorder assessment verified by source document for Visit 2, and subsequently	X	-	X	X	X	

Scenario	Primary LDL-C Analysis	Sensitivity Analyses				
		#1	#2	#3	#4	
*An LDL-C retest will be performed at Visit 2 and used for this analysis.						
^ Missing LDL-C value will be imputed according to missing data imputation method.						
withdraws from trial prior to study completion						
9. Has an “OK to Use” outcome with an LDL-C value entered into the Web App during an early reorder assessment NOT verified by source document for Visit 2 and subsequently withdraws from trial prior to study completion	-	-	X^	X	X	
10. Has an “OK to Use” outcome with an LDL-C value entered into the Web App during an early reorder assessment NOT verified by source document for Visit 2, but at a later reorder gets a “Do Not Use” or “Ask a Doctor” outcome	-	-	X^	X	X	
11. Has an “OK to Use” outcome with an LDL-C value entered into the Web App during an early reorder assessment NOT verified by source document for Visit 2 and refuses a study mandated retest at Visit 2	-	-	X^	X	X	
12. Has “OK to Use” outcome without an LDL-C value entered into the Web App during an early reorder assessment, but gets a “Do Not Use” or “Ask a Doctor” outcome at a subsequent reorder assessment	-	-	X^	-	-	
13. Has “OK to Use” outcome without an LDL-C value entered into the Web App during an early reorder assessment and subsequently withdraws from trial prior to study completion	-	-	X^	-	-	
“Do Not Use” Outcome Scenarios						
1. Has “Do Not Use” outcome with an LDL-C value entered into the Web App during a reorder assessment verified by source document for Visit 2	X	-	X	X	X	
2. Has “Do Not Use” outcome with an LDL-C value entered into the Web App during a reorder assessment verified by source document for Visit 2 and subsequently withdraws from the trial prior to study completion	X	-	X	X	X	
3. Has “Do Not Use” outcome with an LDL-C value entered into the Web App during a reorder assessment NOT verified by source document for Visit 2 and subsequently withdraws from the trial prior to study completion	-	-	X^	X	X	
4. Has “Do Not Use” outcome without an LDL-C value entered into the Web App during a reorder assessment	-	-	X^	-	-	
5. Has “Do Not Use” outcome without an LDL-C value entered into the Web App during a	-	-	X^	-	-	

Scenario	Primary LDL-C Analysis	Sensitivity Analyses				
		#1	#2	#3	#4	
*An LDL-C retest will be performed at Visit 2 and used for this analysis.						
^ Missing LDL-C value will be imputed according to missing data imputation method.						
reorder assessment and subsequently withdraws from the trial prior to study completion						
“Ask a Doctor” Outcome Scenarios						
1. Has an “Ask a Doctor” outcome with an LDL-C value entered into the Web App at the 6-month final use assessment verified by source document for Visit 2	X	X	X	X	X	
2. Has an “Ask a Doctor” outcome with an LDL-C value entered into the Web App at the 6-month final use assessment NOT verified by source document for Visit 2	X*	X*	X*	X*	X	
3. Has “Ask a Doctor” outcome (participant indicates doctor gave permission to use drug) with an LDL-C value entered into the Web App during a reorder assessment verified by source document for Visit 2 and completes the 6-month trial	X	X	X	X	X	
4. Has an “Ask a Doctor” outcome without an LDL-C value entered into the Web App at the 6-month final use assessment	X*	X*	X*	X*	-	
5. Has “Ask a Doctor” outcome (participant indicates doctor gave permission to use drug) without an LDL-C value entered into the Web App during a reorder assessment and completes the 6-month trial	X*	X*	X*	X*	-	
6. Has “Ask a Doctor” outcome (participant does not indicate doctor gave permission to use drug) with an LDL-C value entered into the Web App during a reorder assessment verified by source document for Visit 2	X	-	X	X	X	
7. Has “Ask a doctor” outcome with an LDL-C value entered into the Web App during a reorder assessment verified by source document for Visit 2 and subsequently withdraws from the trial prior to study completion (regardless of whether or not participant had indicated doctor gave permission to use drug)	X	-	X	X	X	
8. Has “Ask a doctor” outcome with an LDL-C value entered into the Web App NOT verified by source document for Visit 2 during a reorder assessment and subsequently withdraws from the trial prior to study completion (regardless of whether or not participant had indicated doctor gave permission to use drug)	-	-	X^	X	X	
9. Has an “Ask a Doctor” outcome with an LDL-	-	-	X^	X	X	

Scenario	Primary LDL-C Analysis	Sensitivity Analyses				
		#1	#2	#3	#4	
*An LDL-C retest will be performed at Visit 2 and used for this analysis.						
^ Missing LDL-C value will be imputed according to missing data imputation method.						
C value entered into the Web App at the 6-month final use assessment NOT verified by source document for Visit 2 and refuses a study mandated retest at Visit 2						
10. Has an “Ask a Doctor” outcome without an LDL-C value entered into the Web App at the 6-month final use assessment and refuses a study mandated retest at Visit 2	-	-	X^	-	-	
11. Has “Ask a Doctor” outcome (participant indicates doctor gave permission to use drug) without an LDL-C value entered into the Web App during a reorder assessment and completes the 6-month trial and refuses a study mandated retest at Visit 2	-	-	X^	-	-	
12. Has “Ask a Doctor” outcome (participant does not indicate doctor gave permission to use drug) without an LDL-C value entered into the Web App during a reorder assessment	-	-	X^	-	-	
13. Has “Ask a doctor” outcome without an LDL-C value entered into the Web App during a reorder assessment and subsequently withdraws from the trial prior to study completion (regardless of whether or not participant had indicated doctor gave permission to use drug)	-	-	X^	-	-

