The acceptable variability for BP measurements is more difficult to ascertain based on a review of the literature. Important factors that could impact variability include the timing of the BP measurement because of the circadian variability in BP, the use of a different device for the participant's inputted BP versus the testing site inputted BP, operator variability when using manual devices, and white coat BP effects. In light of these factors and taking into account that a normal circadian change in BP over the course of 24 hours could be 10% to 20%, we set the acceptable variability for systolic and diastolic BP at 15%.

When applying the variability criteria, the acceptable level of variability will be applied to the CMOG laboratory or BP result to determine if it overlapped with the participant's data. Further details on the process for applying the variability criteria will be found in the SAP.

The acceptable level of variability criteria for the laboratory and BP data will be used to manage the following situations:

- 1 The difference between the laboratory and/or BP data entered by the participant and the one obtained by the testing site was small but was enough to change the assignment of a Risk Enhancing Factor (REF) that was used to determine eligibility for treatment. This will only apply for participants with a 10-yr ASCVD risk score of 5% to <7.5% since those at higher risk do not require a REF.
- 2 The difference between the laboratory and/or BP data entered by the participant and the one obtained by the testing site was small but was enough to take the value outside the treatment range.

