3.2.3.2 Laboratory, Blood Pressure and Waist Circumference Variability Process

Laboratory and BP data are entered by the participant and CMOG into the Web App to generate TASS outcomes at the initial TASS assessment. Since the CMOG will only use verified laboratory and BP data when performing their assessments, and the data used by the CMOG could be different than the data entered by the participant, different TASS outcomes could be generated. In order to address situations where small clinically irrelevant changes in laboratory or BP values lead to different TASS outcomes, acceptable levels of variability for the 10-year Atherosclerotic Cardiovascular Disease (ASCVD) risk score and for the individual laboratory and BP values were established.

The established variability criteria will only be used when assessing the first co-primary endpoint and only when the participant and clinician TASS outcomes at Visit 1 differ because of these values. In other words, if the TASS outcomes for the participant and clinician agree, the laboratory and BP values entered by the participant will be considered acceptable. Note that laboratory and BP data entered into the Web App can only result in either an “OK to Use” or “Do Not Use” outcome. There is no scenario where laboratory or BP values entered into the Web App could lead directly to an “Ask a Doctor” outcome without an “Ask a Doctor” warning being identified during the same assessment.

When applying the variability criteria, the acceptable level of variability will be determined using the CMOG verified data. If the variability in the CMOG’s data encompasses the participant’s data, then that value will be considered acceptable.

The laboratory and BP values determine three important elements of the TASS assessment: the 10-year ASCVD risk score, the presence of a Risk Enhancing Factor (REF) and to determine if the participant’s values are within the appropriate range for treatment. The variability criteria applied when differences in outcomes are observed for each of these elements is provided in [Appendix E](#).

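### First co-primary endpoint: SAP Appendix E accepts a discrepant laboratory or BP value without the comparison with the participant's entry that Protocol 9.4.1.4 and SAP 3.2.3.2 require

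*SAP*

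**What the plan says.** Protocol 9.4.1.4 says that the tolerance "will be applied to the CMOG laboratory or BP result to determine if it overlapped with the" participant's data. One of the two situations it covers is a difference that "was small but was enough to take the value outside the treatment range"; the other is an equally small difference that changes a REF. It adds: "Further details on the process for applying the variability criteria will be found in the SAP".

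SAP 3.2.3.2 gives the purpose as handling cases where "small clinically irrelevant changes in laboratory or BP values lead to different TASS outcomes", and states the test: "If the variability in the CMOG’s data encompasses the participant’s data, then that value will be considered acceptable". It then refers to Appendix E for the criteria.

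Appendix E states a different test. Its treatment-range text reads "If the variability criteria result in a value within the appropriate treatment range, it will be considered acceptable". Step 1 of its procedure applies when the difference is "due solely to a CMOG laboratory or blood pressure value being out-of-range" and concludes: "If the established variability is within treatment range, then the CMOG value is acceptable". The REF text and step 3 work the same way, with the REF cut-off in place of the range. None of these uses the participant's entry. Steps 2 and 3 carry the same sole-cause condition as step 1.

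SAP section 7, on changes from the protocol, is marked not applicable.

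**The concern.** The first co-primary endpoint passes or fails on whether the exact 95% lower bound exceeds 85%. The same participant can be counted correct or incorrect depending on which SAP section is programmed. The Protocol's test asks whether the entry was close to the verified value. Appendix E asks whether the verified value was close to a boundary, so a verified value just outside the range rescues any in-range entry, however far away. That goes beyond the small differences for which the allowance was written.

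There is a second, smaller gap. Each step of Appendix E requires one type of cause. A participant with one value out of range and also a lost REF meets no step, even if SAP 3.2.3.2 would accept each value.

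**Working it through.** **Inputs.** Tolerances (Protocol 9.4.1.4, SAP Appendix E): LDL-C 12%, TG 15%. Do Not Use limits (Appendix E): LDL-C below 70 or at least 190 (men 20-39: below 160 or at least 190); TG at least 500. REF cut-offs: LDL-C 160, TG 175. N is about 1,220, and success needs a Clopper-Pearson lower bound above 85% (SAP 1.3).

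**The plan's own figures first.** The smallest passing count is 1,062 of 1,220 (87.05%): the lower bound is 85.03% at 1,062 and 84.95% at 1,061. Exact power is 90.8% at 88.24%, 95.5% at 88.57%, 98.2% at 88.93% and 99.96% at 90%. The SAP table gives 90%, 95%, 98% and above 99%, so it reproduces.

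**The two rules on the same case.** Band = verified value × (1 ± tolerance).

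| Case | Entry | Verified | Band | Protocol 9.4.1.4 / SAP 3.2.3.2 | Appendix E |
|---|---|---|---|---|---|
| LDL-C range | 100 | 205 | 180.4-229.6 | not acceptable | acceptable (below 190) |
| LDL-C range | 180 | 200 | 176-224 | acceptable | acceptable |
| LDL-C REF | 185 | 150 | 132-168 | not acceptable | acceptable (reaches 160) |
| LDL-C REF | 165 | 150 | 132-168 | acceptable | acceptable |

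**Direction when there is one cause.** The participant qualified, so the entry lies in range or meets the cut-off. A band that contains the entry therefore always reaches the range or cut-off. Every acceptance under the Protocol rule is also one under Appendix E, but not the reverse. On a whole-number grid for the LDL-C upper limit (verified 190-259, entry 70-189), no pair passes the Protocol rule only, 294 pass both and 2,826 pass Appendix E only. These count grid points, not participants.

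**Verified values at which the rules can differ.**
- LDL-C range 70-189: 63-69 (63 × 1.12 = 70.6) and about 190-215 (215 × 0.88 = 189.2).
- LDL-C 143-159: a range case for men 20-39, and the LDL-C REF case (143 × 1.12 = 160.2).
- TG range: 500 to about 588 (588 × 0.85 = 499.8).
- TG REF: 153-174 (153 × 1.15 = 176.0).

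The list is not exhaustive. The other range parameters, and metabolic-syndrome REFs lost on one criterion, are affected in the same way.

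**Effect on the verdict.** Extra acceptances can turn a fail into a pass only if the count under the Protocol rule is below 1,062. One is enough at 1,061, 7 at 1,055 (86.5%), 13 at 1,049 (86.0%) and 25 at 1,037 (85.0%). The chance of a count below 1,062 is 1 minus power: 9.2% at 88.24%, 4.5% at 88.57% and 0.04% at 90%.

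**Combined causes.** Take a non-diabetic man aged 40-75 with an ASCVD score of 5% to below 7.5%. LDL-C is entered as 70 and verified as 69: out of range, with band 69 × 0.88 = 60.7 to 69 × 1.12 = 77.3. TG is entered as 178 and verified as 170: his only REF is lost, with band 144.5 to 195.5. Both bands contain the entries, so SAP 3.2.3.2 accepts both values. Neither step 1 nor step 3 applies, because neither cause is the sole one. By default, SAP Figure 1 leaves OK to Use against Do Not Use as Incorrect Selection.

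**The case against.** The best defence is that a boundary test suits this endpoint. The endpoint measures agreement on eligibility, not accuracy of numbers. When the outcomes agree, the plan accepts the laboratory values however far apart they are, and the ASCVD rule accepts on the clinician's score alone. The Protocol leaves process detail to the SAP, and SAP 3.2.3.2 points to Appendix E. Appendix E could also be read as a further check on top of SAP 3.2.3.2.

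It stands that the boundary test is a defensible choice. It does not stand that the documents have made it. The Protocol itself states the overlap test, SAP 3.2.3.2 repeats it, and section 7 declares no change. Steps 1 and 3 end in acceptance without the comparison, so someone following the procedure would not make it. The ASCVD rule is set by the Protocol itself and is not in dispute.

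Three stronger readings are tempting but not supported:
- *Appendix E refuses cases where several values together lose one REF, as in metabolic syndrome.* Step 3's condition refers to laboratory or BP data as a whole, its conclusions are in the plural, and the range text allows for more than one value. Such cases can be read as covered.
- *Combined causes have no classification.* Figure 1 supplies a default, and remaining incorrect outcomes are reviewed for post-study mitigation.
- *No planned estimate leaves these acceptances out.* The documents do not say whether they are coded as mitigations. If they are, the analysis without any mitigations in SAP 4.2.2 already removes them.

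**Conclusion.** Appendix E is wrong as written. For a difference due solely to a laboratory or BP value being out of range or not generating a REF, its acceptance rule is looser than the one in Protocol 9.4.1.4 and SAP 3.2.3.2. In those cases it can only add successes to the first co-primary endpoint.

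A reader might infer that the endpoint is inflated overall. The documents do not support that: they do not give the number of affected participants, and the sole-cause conditions can remove successes in cross-step combinations, so the net direction is unknown. The probabilities of 9.2% and 0.04% are ceilings on how often extra acceptances could change the verdict. They assume N = 1,220 and that the stated rate is the true rate under the Protocol rule. At 90% the issue makes no practical difference; near the pass mark a handful of cases would decide the result. It should be fixed, because the choice of rule should not be left to the programmer.

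**What to change.** In Appendix E (range text, REF text, steps 1 and 3), accept a value only if the verified value plus or minus tolerance includes the value the participant entered. Apply this to each value that caused the lost range or REF status. The plan already compares waist circumference with the participant's own figure, at 6.5%, when the two measurements disagree on the criterion.

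For combinations across steps, accept only if every contributing cause passes its own step. Keep judging the ASCVD score by the 4% floor on the clinician's score, and do not substitute the participant's TC, HDL-C or SBP into it; substitution could let a case that fails the floor alone pass once it has a second problem.

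If the boundary test is what the sponsor intends, amend Protocol 9.4.1.4 and SAP 3.2.3.2 and list the change in SAP section 7.

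In either case, state whether variability acceptances count as mitigations, make sure one planned estimate of the first co-primary endpoint excludes them, and report how many participants the two rules classify differently.

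The cost is SAP wording, a programming condition for discrepant cases and an added column in an existing table, with no new data. Some genuine older entries that changed biologically would count as incorrect. That follows from the plan's own choice to rely on analytical variability alone for laboratory values.
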